3.1 Primary estimands

The primary clinical question of interest is: What is the probability that [⁶⁸Ga]Ga-DOTA-TATE PET/CT imaging truly detects tumor lesion(s) in subject-level for NENs using CIM (including [¹¹¹In]In-Pentetreotide SPECT/CT and High Resolution CT with contrast (or MRI if CT with contrast is medically contraindicated) as standard of truth).

The justification for the primary estimand is that it will capture the diagnostic performance of [⁶⁸Ga]Ga-DOTA-TATE PET/CT imaging in detecting tumor lesion(s) in NENs subjects. For this reason, participants with confirmed or suspected NENs will be investigated with CIM obtained on or before screening phase (HVs will be categorized as CIM negative without performing CIM) and confirmed or suspected NENs and HVs will be investigated with [⁶⁸Ga]Ga-DOTA-TATE PET/CT imaging on treatment phase, and the results of [⁶⁸Ga]Ga-DOTA-TATE PET/CT imaging will be compared against the results of CIM as standard of truth.

The primary estimands are described by the following attributes:

Primary estimand 1:

1. Population: Patients who show at least one lesion based on CIM by central read, received [⁶⁸Ga]Ga-DOTA-TATE, completed a PET/CT scan and had a central read of the [⁶⁸Ga]Ga-DOTA-TATE PET/CT imaging.
2. Variable: The result of [⁶⁸Ga]Ga-DOTA-TATE PET/CT imaging (positive (i.e., showing at least one lesion) or negative (i.e., not showing any lesion)). In the population above, a participant with positive [⁶⁸Ga]Ga-DOTA-TATE PET/CT imaging corresponds to True positive (TP) and a participant with negative on [⁶⁸Ga]Ga-DOTA-TATE PET/CT imaging corresponds to False negative (FN).
3. Treatment of interest: [⁶⁸Ga]Ga-DOTA-TATE injected as a single intravenous dose of 2 MBq/kg (0.054 mCi/kg) of body weight up to a maximum total dose of 200 MBq (5.4 mCi).
4. Intercurrent events: None
5. Summary measure: Estimate of proportion of participants who test positive on [⁶⁸Ga]Ga-DOTA-TATE PET/CT imaging (TP) among those who are CIM positive (TP+FN)

according to [⁶⁸Ga]Ga-DOTA-TATE PET/CT imaging) (subject-level sensitivity), along with 95% confidence interval.

Primary estimand 2:

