6.3.2 Treatment blinding

The following blinding is applicable in this study:

- [⁶⁸Ga]Ga-DOTA-TATE PET/CT imaging will be submitted to a CRO for independent centralized read by 3 independent readers blinded to CIM and patient data collected in clinical database.
- CIM will be submitted to a CRO for independent centralized read by 1 independent reader, blinded to [⁶⁸Ga]Ga-DOTA-TATE PET/CT imaging and patient data collected in clinical database.

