1.2.1 Primary estimand(s)

The primary clinical question of interest is: What is the probability that [⁶⁸Ga]Ga-DOTA-TATE PET/CT imaging truly detects tumor lesion(s) in subject-level for NENs using CIM (including [¹¹¹In]In-Pentetreotide SPECT/CT and High Resolution CT with contrast (or MRI if CT with contrast is medically contraindicated) as standard of truth).

The justification for the primary estimand is that it will capture the diagnostic performance of [⁶⁸Ga]Ga-DOTA-TATE PET/CT imaging in detecting tumor lesion(s) in NENs subjects. For this reason, participants with confirmed or suspected NENs will be investigated with CIM obtained on or before screening phase (HVs will be categorized as CIM negative without performing CIM) and confirmed or suspected NENs and HVs will be investigated with [⁶⁸Ga]Ga-DOTA-TATE PET/CT imaging on treatment phase, and the results of [⁶⁸Ga]Ga-DOTA-TATE PET/CT imaging will be compared against the results of CIM as standard of truth. The primary estimands are described by the following attributes:

Primary estimand 1:

1. Population: Patients who show at least one lesion based on CIM by central read, received [⁶⁸Ga]Ga-DOTA-TATE, completed a PET/CT scan and had a central read of the [⁶⁸Ga]Ga-DOTA-TATE PET/CT imaging.
2. Variable: The result of [⁶⁸Ga]Ga-DOTA-TATE PET/CT imaging (positive (i.e., showing at least one lesion) or negative (i.e., not showing any lesion)). In the population above, a participant with positive on [⁶⁸Ga]Ga-DOTA-TATE PET/CT imaging corresponds to True positive (TP) and a participant with negative on [⁶⁸Ga]Ga-DOTA-TATE PET/CT imaging corresponds to False negative (FN).
3. Treatment of interest: [⁶⁸Ga]Ga-DOTA-TATE injected as a single intravenous dose of 2 MBq/kg (0.054 mCi/kg) of body weight up to a maximum total dose of 200 MBq (5.4 mCi).
4. Intercurrent events: None
5. Summary measure: Estimate of proportion of participants who test positive on [⁶⁸Ga]Ga-DOTA-TATE PET/CT imaging (TP) among those who are CIM positive (TP+FN according to [⁶⁸Ga]Ga-DOTA-TATE PET/CT imaging) (subject-level sensitivity), along with 95% confidence interval.

Primary estimand 2:

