2.5.1 Primary endpoint(s)

The co-primary endpoints of the study are subject-level sensitivity and specificity.

Subject-level sensitivity

Subject-level sensitivity is defined as the proportion of $[^{68}\text{Ga}]\text{Ga}\text{-DOTA-TATE}$ PET/CT imaging positive participants (i.e. TP participants) among CIM positive participants (i.e. TP or FN participants).

Subject-level specificity

Subject-level specificity is defined as the proportion of $[^{68}\text{Ga}]\text{Ga}\text{-DOTA-TATE}$ PET/CT imaging negative participants (i.e. TN participants) among CIM negative participants (i.e. TN or FP participants).

Table 2-2 Sensitivity and Specificity

		Conventional Imaging (CIM)	
		Positive	Negative
$[^{68}\text{Ga}]\text{Ga}\text{-DOTA-TATE}$ PET/CT imaging	Positive	True Positive (TP)	False Positive (FP)
	Negative	False Negative (FN)	True Negative (TN)
Sensitivity: TP / (TP + FN), Specificity: TN / (TN + FP)			

Where TP, FP, TN, FN participants are defined as follows:

- TP participants are those who show at least one lesion based on both $[^{68}\text{Ga}]\text{Ga}\text{-DOTA-TATE}$ PET/CT imaging and CIM by central read.
- FP participants are those who show at least one lesion based on $[^{68}\text{Ga}]\text{Ga}\text{-DOTA-TATE}$ PET/CT imaging but do not show any lesion based on CIM by central read.
- TN participants are those who do not show any lesion based on both $[^{68}\text{Ga}]\text{Ga}\text{-DOTA-TATE}$ PET/CT imaging and CIM by central read.

- FN participants are those who do not show any lesion based on [⁶⁸Ga]Ga-DOTA-TATE PET/CT imaging but show at least one lesion based on CIM by central read.

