2.6.1 Secondary endpoint(s)

Subject-level assessments

Subject-level positive predictive values (PPV) is defined as the proportion of TP participants among $[^{68}\text{Ga}]\text{Ga}\text{-DOTA-TATE}$ PET/CT imaging positive participants (i.e. TP or FP participants).

Subject-level negative predictive values (NPV) is defined as the proportion of TN participants among $[^{68}\text{Ga}]\text{Ga}\text{-DOTA-TATE}$ PET/CT imaging negative participants (i.e. TN or FN participants).

Subject-level accuracy is defined as the proportion of TP and TN participants among all patients in the EFF (i.e. TP+TN+FP+FN participants).

Region-level assessments

Region-level sensitivity is defined as the proportion of $[^{68}\text{Ga}]\text{Ga}\text{-DOTA-TATE}$ PET/CT imaging positive regions (TP regions) among CIM positive regions (i.e. TP or FN regions).

Region-level specificity is defined as the proportion of $[^{68}\text{Ga}]\text{Ga}\text{-DOTA-TATE}$ PET/CT imaging negative regions (TN regions) among CIM negative regions (i.e. TN or FP regions).

Region-level PPV is defined as the proportion of regions which are positive on both $[^{68}\text{Ga}]\text{Ga}\text{-DOTA-TATE}$ PET/CT imaging and CIM (TP regions) among $[^{68}\text{Ga}]\text{Ga}\text{-DOTA-TATE}$ PET/CT imaging positive regions (i.e. TP or FP regions).

Region-level NPV is defined as the proportion of regions which are negative on both $[^{68}\text{Ga}]\text{Ga}\text{-DOTA-TATE}$ PET/CT imaging and CIM (TN regions) among $[^{68}\text{Ga}]\text{Ga}\text{-DOTA-TATE}$ PET/CT imaging negative regions (i.e. TN or FN regions).

Region-level accuracy is defined as the proportion of regions which are CIM and $[^{68}\text{Ga}]\text{Ga}\text{-DOTA-TATE}$ PET/CT imaging positive (TP regions) or negative (TN regions) among regions detected by CIM and $[^{68}\text{Ga}]\text{Ga}\text{-DOTA-TATE}$ PET/CT imaging (i.e. TP+TN+FP+FN regions).

Where TP, FP, TN, FN regions are defined as follows:

- TP regions are the regions which show at least one lesion based on both $[^{68}\text{Ga}]\text{Ga}\text{-DOTA-TATE}$ PET/CT imaging and CIM by central read.
- FP regions are the regions which show at least one lesion based on $[^{68}\text{Ga}]\text{Ga}\text{-DOTA-TATE}$ PET/CT imaging but do not show any lesion based on CIM by central read.
- TN regions are the regions which do not show any lesion based on both $[^{68}\text{Ga}]\text{Ga}\text{-DOTA-TATE}$ PET/CT imaging and CIM by central read.

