2.6.2 Statistical hypothesis, model, and method of analysis

Subject-level assessments

Subject-level PPV, NPV, accuracy will be summarized with corresponding exact 95% CI.

Region-level assessments

Region-level sensitivity, specificity, PPV, NPV, accuracy will be summarized respectively with corresponding exact 95% CI by regions.

Region consists of liver, pancreas, gastrointestinal, lymph nodes and others.

Number of lesions detected by imaging

Descriptive statistics for number of lesions will be provided by region-level and subject-level.

Regarding [⁶⁸Ga]Ga-DOTA-TATE PET/CT imaging, descriptive statistics of number of lesions for each of the 3 central reader , and 3 readers' mean number of lesions will be presented.

Regarding CIM, descriptive statistics of number of lesions detected by [¹¹¹In]In-Pentetreotide SPECT/CT and High Resolution CT with contrast (or MRI if CT with contrast is medically contraindicated) will be presented respectively.

Listing for number of lesions will be provided.

Impact on treatment decision

The number (%) of participants for intended treatment plan at pre and post [⁶⁸Ga]Ga-DOTA-TATE PET/CT imaging and the number (%) of participants for whom the intended treatment plan has changed and for whom it has not changed will be summarized. The number (%) of

participants will also be summarized for each combination of transition of intended treatment plan.

Listing for intended treatment plan will be provided.

Inter-reader variability

Each central read subject-level result (positive or negative), inter-reader variability (%) and its 95% CI will be presented.

Inter-reader variability will be assessed by Fleiss' Kappa (κ_1) statistic ([Fleiss 1971](#)). Refer to [Section 5.4.2](#) for details on Fleiss' Kappa.

An additional table will be presented to show the distribution of agreements with the number (%) of scans agreed by two readers and the number (%) of scans agreed by all three readers.

If one of the central readers is changed during the study and the total amount of its read is more than 30% of the total number of participants who have evaluable [⁶⁸Ga]Ga-DOTA-TATE PET/CT, inter-reader variability for each combination (before the change and after the change) and its normality 95% CI will be presented additionally. The distribution of agreements with the number (%) of scans agreed by two readers and the number (%) of scans agreed by all three readers will be also presented for each combination.

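### The subject-level true positive requires no location match, so the co-primary sensitivity can include patients whose PET missed every CIM lesion; a region-matched sensitivity should be reported beside it

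*SAP*

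**What the plan says.** The primary question, in Protocol 3.1 and SAP 1.2.1, is the probability that PET "truly detects tumor lesion(s) in subject-level for NENs using CIM" as the standard of truth. The variable for estimand 1 is the whole-subject PET result: "positive (i.e., showing at least one lesion) or negative (i.e., not showing any lesion".

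SAP 2.5.1, which matches Protocol 9.3.1, turns this into counts. "TP participants are those who show at least one lesion based on both" modalities by central read. In the other direction, "FN participants are those who do not show any lesion based on" PET although CIM shows one. Only a PET with no lesion anywhere is a miss.

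The PET images go to "3 independent readers blinded to CIM and patient data collected in clinical database" (Protocol 6.3.2), and the CIM reader is blinded to PET. Protocol 10.1.4.3 has no adjudication committee.

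Location enters only in the secondary analyses. SAP 2.6.1 says "TP regions are the regions which show at least one lesion based on both" modalities, and SAP 2.6.2 says "Region consists of liver, pancreas, gastrointestinal, lymph nodes and others". Those results are given region by region with exact CIs and carry no threshold. The supplementary analyses of the primary endpoint (SAP 2.5.6) contain no location-matched version and run only if the co-primary endpoints are met.

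**The concern.** Take a patient with a liver lesion on CIM that PET does not show, and a lymph-node lesion on PET that CIM does not show. Under the region rules this patient contributes a false-negative liver region and a false-positive lymph-node region. At subject level the same patient is a true positive.

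The plan also treats an unconfirmed PET lesion in two ways. In a CIM-negative participant it is a false positive and lowers specificity. In a CIM-positive participant whose CIM lesions were all missed, it turns a false negative into a true positive and raises sensitivity.

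Mutual blinding of the readers is proper, but it means that location can be compared only in the analysis, and the primary analysis has no such step. The by-region tables do not fill the gap. The share of patients with at least one matched region needs linkage within patient, which separate regional proportions do not carry. The report would not show how much of the co-primary sensitivity rests on unmatched findings.

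**Working it through.** **Inputs from the documents.** Sensitivity: expected 0.90, threshold 0.70, n = 47 CIM-positive participants. Specificity: expected 0.90, threshold 0.60, n = 23 CIM-negative participants. One-sided alpha is 2.5%, exact binomial (Protocol 9.9.1, SAP 3). Success means that the Clopper-Pearson lower bound exceeds 0.70 for sensitivity and 0.60 for specificity (SAP 2.5.2).

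**Plan's own figure.** With n = 47, 40 positives give a lower bound of 0.717 and 39 give 0.692, so success needs at least 40. P(X ≥ 40 | 47, 0.70) = 1.38%. P(X ≥ 40 | 47, 0.90) = 90.72%, against 90.7% stated. All twelve powers in SAP Table 3-1 reproduce. The sample-size arithmetic is sound.

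**Model.** Let m be the matched sensitivity. Let q be the chance that a CIM-positive participant with no matched PET lesion has a PET lesion elsewhere. Then

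scored sensitivity = m + (1 − m) × q.

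The documents do not give q, so a range is shown. For scale only, the specificity assumption of 90% and threshold of 60% correspond to false-positive rates of 10% and 40%, in a CIM-negative group made up mostly of healthy volunteers.

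**Matched sensitivity at the threshold, m = 0.70.** The specificity and joint columns add two assumptions: the same q applies in CIM-negative participants, so specificity is 1 − q, and the two groups are independent. With n = 23, specificity needs at least 19 negatives.

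| q | Scored sensitivity | Sensitivity objective met | Specificity objective met | Both met |
|---|---|---|---|---|
| 0 | 0.700 | 1.4% | 100% | 1.4% |
| 5% | 0.715 | 2.3% | 99.5% | 2.3% |
| 10% | 0.730 | 3.8% | 92.7% | 3.6% |
| 20% | 0.760 | 9.4% | 50.1% | 4.7% |
| 40% | 0.820 | 37.2% | 1.9% | 0.7% |

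The joint figure is the product of the two columns before it, for example 0.0940 × 0.5007 = 0.047. For the matched quantity, the sensitivity objective alone passes the nominal 2.5% at a q of about 6%.

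**Matched sensitivity at the planned value, m = 0.90.** With q = 10%, scored sensitivity is 0.90 + 0.10 × 0.10 = 0.91. Power for the sensitivity objective is 94.3% instead of 90.7%.

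**The case against.** The strongest reply is that the definition is explicit and the same in the estimand, the protocol and the SAP, and that the question is asked at subject level. An any-lesion rule answers whether a patient is called positive; a matched rule is a different estimand. This stands. The definition is not a mistake and need not be replaced.

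Second, an off-CIM PET lesion may be real tumour. Protocol 2.3 expects that new lesions may be found, and Protocol 2.2 cites additional PET lesions in patients with negative or equivocal pentetreotide scans. This also stands. An unmatched true positive is a discordance with the declared truth that is scored as agreement, and not necessarily a wrong call.

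Third, a reader might infer from the 37% that the trial could easily succeed with a poor test. The documents do not support that. The figure concerns one of two objectives that must both be met, at an assumed q of 40%. If that rate also held in CIM-negative participants, specificity would almost always fail. Equal q in the two groups is itself an assumption, so the joint figures are a guide and not a bound.

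Fourth, location is partly covered already by the regional results, the lesion counts by region and the FAS listing of central reads, none of which depends on the primary being met. A reader could trace discordance in the listing, but no planned summary gives the matched rate per patient.

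Finally, the Imaging Manual was not available, so a matching rule there cannot be excluded. Neither the protocol nor the SAP contains one.

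**Conclusion.** The point holds as a gap in reporting. Matched true positives are a subset of scored true positives, so the absence of a location condition can only raise the co-primary sensitivity relative to a region-matched result. The size is unknown because q is unknown. The effect is small if q is 5% or less, or if sensitivity is near the planned 0.90. It matters for the sensitivity objective when matched sensitivity is near 0.70 and q is 10% or more, with the specificity objective as a partial safeguard if off-target calls are equally common in CIM-negative participants.

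Two stronger readings are not supported: that the primary definition is invalid, and that every unmatched finding is a false detection. What is justified is a prespecified supplementary result that shows how many true positives are unmatched.

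**What to change.** Keep the primary definition and decision rule. Add to SAP 2.5.6 a region-matched subject-level sensitivity with exact 95% CI, reported whether or not the co-primary endpoints are met:

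- **TP:** at least one of the five regions is positive on both PET and CIM.
- **FN:** any other CIM-positive participant, with the exception below.
- **Not evaluable for this analysis, shown separately:** no matched region, and at least one CIM-positive region unreadable on PET. SAP 2.2 keeps a participant with an unreadable region in the EFF if another region is positive, so this case can occur and should not be scored as a miss.
- **Readers:** combine the three PET readers by the same rule as in the primary analysis, and also show each reader. SAP 2.5 does not spell that rule out, so it should be stated here.
- **Count:** report the number of primary true positives that are unmatched.

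The cost is one derived variable and a few table rows, from region-level central reads already planned. The figure may be slightly lower than the primary. Because the regions are broad and the PET and CIM readers are blinded to each other, one lesion near a boundary can be assigned to two different regions and count as a miss, while unrelated sites within the category for other regions can count as a match. The result should therefore be labelled region-matched and not lesion-matched.

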2.5.2 Statistical hypothesis, model, and method of analysis

To address the co-primary objectives, following analyses will be conducted.

Subject-level sensitivity and its 95% exact confidence interval (CI) will be calculated based on the binomial distribution. The lower bound of the 95% exact CI for subject-level sensitivity should be greater than 0.7 to attain the first co-primary objective.

Subject-level specificity and its 95% exact CI will be calculated based on the binomial distribution. The lower bound of the 95% exact CI for subject-level specificity should be greater than 0.6 to attain the second co-primary objective.

Listing for central imaging assessments will be provided for the FAS.

2.5.3 Handling of intercurrent events

Not applicable.

2.5.4 Handling of missing values not related to intercurrent event

This is a diagnostic study and primary endpoints are calculated on the basis of [⁶⁸Ga]Ga-DOTA-TATE PET/CT imaging and CIM assessments. The primary analysis will be conducted for the EFF and missing data related to primary endpoints will not occur in the population.

2.5.5 Sensitivity analyses

Not applicable.

2.5.6 Supplementary analyses

If the primary endpoints of subject-level sensitivity and specificity are met, following supplementary analyses will be conducted.

- TP, FP, FN, TN, sensitivity, specificity and corresponding exact 95% CIs will be shown for each of the 3 central readers.
- If there are participants who are excluded from the EFF, those participants' results will be assumed all positive or all negative respectively and each analysis will be performed for primary endpoints. Assumption of handling as all negative will be conservative for sensitivity and assumption of handling as all positive will be conservative for specificity.
- If there are participants with readable but not optimal [⁶⁸Ga]Ga-DOTA-TATE PET/CT imaging, analysis excluding those participants will be repeated for primary endpoints. If at least one reader reports readable but not optimal, then the imaging of the participant will be considered readable but not optimal.
- The subgroup analyses estimating subject-level sensitivity or specificity with corresponding exact 95% CIs will be performed. Subgroups of interest are specified in [Section 2.2.1](#).

2.6 Analysis supporting secondary objectives

All analyses supporting secondary objectives will be performed for the EFF.

2.6.1 Secondary endpoint(s)

Subject-level assessments

Subject-level positive predictive values (PPV) is defined as the proportion of TP participants among $[^{68}\text{Ga}]\text{Ga}\text{-DOTA-TATE}$ PET/CT imaging positive participants (i.e. TP or FP participants).

Subject-level negative predictive values (NPV) is defined as the proportion of TN participants among $[^{68}\text{Ga}]\text{Ga}\text{-DOTA-TATE}$ PET/CT imaging negative participants (i.e. TN or FN participants).

Subject-level accuracy is defined as the proportion of TP and TN participants among all patients in the EFF (i.e. TP+TN+FP+FN participants).

Region-level assessments

Region-level sensitivity is defined as the proportion of $[^{68}\text{Ga}]\text{Ga}\text{-DOTA-TATE}$ PET/CT imaging positive regions (TP regions) among CIM positive regions (i.e. TP or FN regions).

Region-level specificity is defined as the proportion of $[^{68}\text{Ga}]\text{Ga}\text{-DOTA-TATE}$ PET/CT imaging negative regions (TN regions) among CIM negative regions (i.e. TN or FP regions).

Region-level PPV is defined as the proportion of regions which are positive on both $[^{68}\text{Ga}]\text{Ga}\text{-DOTA-TATE}$ PET/CT imaging and CIM (TP regions) among $[^{68}\text{Ga}]\text{Ga}\text{-DOTA-TATE}$ PET/CT imaging positive regions (i.e. TP or FP regions).

Region-level NPV is defined as the proportion of regions which are negative on both $[^{68}\text{Ga}]\text{Ga}\text{-DOTA-TATE}$ PET/CT imaging and CIM (TN regions) among $[^{68}\text{Ga}]\text{Ga}\text{-DOTA-TATE}$ PET/CT imaging negative regions (i.e. TN or FN regions).

Region-level accuracy is defined as the proportion of regions which are CIM and $[^{68}\text{Ga}]\text{Ga}\text{-DOTA-TATE}$ PET/CT imaging positive (TP regions) or negative (TN regions) among regions detected by CIM and $[^{68}\text{Ga}]\text{Ga}\text{-DOTA-TATE}$ PET/CT imaging (i.e. TP+TN+FP+FN regions).

Where TP, FP, TN, FN regions are defined as follows:

- TP regions are the regions which show at least one lesion based on both $[^{68}\text{Ga}]\text{Ga}\text{-DOTA-TATE}$ PET/CT imaging and CIM by central read.
- FP regions are the regions which show at least one lesion based on $[^{68}\text{Ga}]\text{Ga}\text{-DOTA-TATE}$ PET/CT imaging but do not show any lesion based on CIM by central read.
- TN regions are the regions which do not show any lesion based on both $[^{68}\text{Ga}]\text{Ga}\text{-DOTA-TATE}$ PET/CT imaging and CIM by central read.
- FN regions are the regions which do not show any lesion based on $[^{68}\text{Ga}]\text{Ga}\text{-DOTA-TATE}$ PET/CT imaging but show at least one lesion based on CIM by central read.

Number of lesions detected by imaging

Number of lesions is defined as number of lesion identified at [⁶⁸Ga]Ga-DOTA-TATE PET/CT imaging and each CIM (i.e. [¹¹¹In]In-Pentetreotide SPECT/CT and High Resolution CT with contrast (or MRI if CT with contrast is medically contraindicated)).

Impact on treatment decision

Impact on treatment decision is defined as change of intended treatment plan collected from physician at pre and post [⁶⁸Ga]Ga-DOTA-TATE PET/CT imaging.

Inter-reader variability

Inter-reader variability for [⁶⁸Ga]Ga-DOTA-TATE PET/CT imaging is defined as agreement rate among reader determinations assessed by Fleiss' Kappa statistics.

Lesion-level concordance rate for SSTR

Lesion-level concordance rate for SSTR is defined as the proportion of lesions which are positive or negative on both local read of [⁶⁸Ga]Ga-DOTA-TATE PET/CT imaging and local histopathology among lesions detected by local histopathology.

